# **10.3 Secondary Analyses**

The following objectives will be addressed for all IBD patients:

- In order to characterize socio-demographic and clinical aspects of moderate to severe IBD, a summary table with the descriptive statistics of the selected variables, by CD and UC patients.
- Descriptive statistics will also be used to summarize treatment patterns for CD and UC in the previous 3 years, including the use of biologic therapies and failure to these therapies (if any), time between IBD diagnosis and initial treatment, first treatment after diagnosis of moderate to severe IBD, among other variables of interest.
- Within CD and UC groups, the patients with moderate to severe disease activity will be compared with patients with mild or no activity, regarding socio-demographic, clinical and treatment variables of interest:

Chi-square or Fisher exact tests will be used to compare qualitative variables, such as gender, smoking habits, professional status, family history of IBD, steroid behavior (dependent/refractory), previous treatment with biologic therapies, and previous surgery for IBD, among others.

Property of Tak The t-student or Mann-Whitney tests will be used for comparison of quantitative variables, such as age, time since diagnosis, and duration of treatment, among others.

is of Use

- If applicable, logistic regression models (for CD and UC patients) will be used to identify independent variables associated with disease control at Day 1, and odds ratios (OR) with 95% CI will be presented.
- Within CD and UC groups, the patients with moderate to severe disease activity will be compared with patients with mild or no activity, regarding socio-demographic, clinical and treatment variables of interest.
- For each IBD disease, descriptive statistics mean, standard-deviation (SD), median, minimun, maximun - will be used to summarize patients' QoL, overall and according to disease activity
  - The score of EQ-5D analog scale and responses to each item. 0
    - Utilities will be configured such that 0.0 is associated with being dead and 1.0 is associated with perfect health; thus, a higher utility value is considered better. Mean (SD) utility index will be estimated for CD and UC patients, overall and according to disease activity.
  - The SF-36 uses 36 items to evaluate eight health dimensions: 0
    - Physical functioning (PF) Average of Q3a, Q3b, Q3c, Q3d, Q3e, Q3f, Q3g, Q3h, Q3i and Q3j scores;

(Mean (SD) impairment while working due to IBD. The percentage of impairment while working due to IBD will be calculated for each subject as Q5/10\*100

- Mean (SD) total activity impairment due to IBD. The percentage of total activity impairment due to IBD will be calculated for each subject as Q6/10 \*100
- Additionaly, the proportions of patients reporting some absenteeism, some work impairment, and some activity impairment due to IBD will be presented.

- Patients with moderate to severe disease will be compared with patients with no or mild disease regarding WPAI data (percent total work productivity impairment due to IBD, percent work time missed due to IBD, percent impairment while working due to IBD and percent total activity impairment due to IBD) through the t-test for independent samples or Mann-Whitney test in case of non-normality of the quantitative variable distribution.
- Healthcare resources (previous 3 years) will be described by IBD group and by disease activity, for the following events: drug therapies, number and type of imaging and laboratory testing, surgeries, number, reason and duration of hospitalizations, number and type of consultations with gastroenterologists or other medical specialists and adverse events.
- Healthcare resource costs: costs will be reported in total and on a *per patient per month* basis. Costs will be obtained by multiplying resource use with relevant unit costs. Unit costs for resource items will be collected in Argentine reliable administrative databases or other sources.
  - UC or CD-related health care costs. Consumer price index (CPI)-adjusted IBD-related health care costs will be computed as total costs, medical costs, drug costs, and other costs.
  - Treatment pattern costs. Treatment pattern costs will be calculated as total UC or CD-related health care costs, stratified by the defined treatment patterns. In addition to the descriptive cost data, multivariate cost models may be developed where the observation time is divided into intervals of equal length.

# **10.4 Interim Analyses**

No interim analyses are planned for this study.

# 10.5 Handling of missing data

Given that all analyses are descriptive in nature, no imputation of missing data will be performed, except when detailed in the SAP regarding the PRO tools.

# **10.6 Determination of Sample Size**

re of use It is expected to include 246 patients regardless of IBD type. This sample size will allow estimates with 95% confidence interval and a margin of error less than 5% and assuming a rate of inadequate control of disease of 20% (conservative approach), regardless of IBD type.

The following formula was used:

$$n = \frac{1.96^2 \times p \times (1-p)}{ME^2}$$

Rate of uncontrolled disease (p) = 20%

Margin of error (ME) = 0.05

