### Primary Objective:

To evaluate the proportion of moderate to severe IBD patients with active disease at Day 1 (active Crohn's Disease (CD) defined as Harvey Bradshaw Index (HBI) score  $\geq 8$  or Crohn's Disease Activity Index (CDAI) ≥ 220 points; active Ulcerative Colitis (UC) defined as 9-point partial Mayo  $\geq 5$ ).

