### Number of subjects

It is expected to include 246 patients regardless of IBD type.

This sample size will allow estimates with 95% confidence interval and a margin of error less than 5%, and assuming a rate of inadequate control of disease of 20% (conservative approach), regardless of IBD type. The following formula was used:

and

$$n = \frac{1.96^2 \times p \times (1-p)}{ME^2}$$

Rate of uncontrolled disease (p) = 20%Margin of error (ME) = 0.05

Expected recruitment period: 6 months

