### Main outcome variables

### Primary Endpoints:

- For Crohn's Disease: Proportion of patients with active disease (HBI  $\ge$  8 or CDAI  $\ge$  220 points based on criteria used by the site) at Day 1.
- For Ulcerative Colitis: Proportion of patients with active disease (9-point partial Mayo  $\geq$ 5) at Day 1.

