#### 10.1.1 **Study Endpoints**

The main study endpoints are:

Primary Endpoints:

- For Crohn's Disease: Proportion of patients with active disease (HBI ≥8 or CDAI ≥220 points based on criteria used by the site) at Day 1.
- For Ulcerative Colitis: Proportion of patients with active disease (9-point partial Mayo score  $\geq$ 5) at Day 1.

Secondary Endpoints:

- Distribution of age, gender, smoking habits, professional status, family history, educational level, subject income, by IBD type.
- Distribution of clinical variables (steroid behaviour, anthropometric information, medical history and comorbidities, clinical presentation of disease) by IBD type.

Therapies for IBD (aminosalicylates, steroids, immunomodulators, immunossupressors, biologics, antibiotics, probiotics, surgeries) and the length of these therapies during the previous 3 years.

- Proportion of biologic-experienced patients.
- Proportion of patients who have not responded previously to biologic therapies and reason.
- IBD treatment introduced at Day 1 (if applicable).

- Socio-demographic, clinical and treatment-related variables in patients with moderate to severe activity of CD (HBI  $\ge 8$  or CDAI  $\ge 220$  points) versus patients with mild or no activity (HBI < 8

- ect to the app function and social function).
- Mean total percentage of work impairment (WPAI). •
- Mean work time missed (WPAI).
- Mean impairment while working (WPAI). •
- Mean total activity impairment (WPAI). •
- Proportion of patient who quit their job due to IBD and have not been able to return to work.
- Healthcare resources (previous 3 years) imaging and laboratory testing, surgeries, hospitalizations se only and consultations.

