# **10.2 Primary Analyses**

Terms of Use For Crohn's Disease (CD), the proportion of patients with active disease at Day 1 will be presented as percentage and calculated as:

$$\frac{\textit{CD patients with HBI} \ge 8 \text{ or CDAI} \ge 220}{\textit{Total CD patients}} x 100$$

.1 bey 0 applica 0, the application of the applicat For Ulcerative Colitis (UC), the proportion of patients with active disease at Day 1 will be presented as percentage and calculated as:

 $\frac{UC \text{ patients with partial Mayo score} \geq 5}{Total UC \text{ patients}}$ 

The 95% confidence intervals will be computed for each estimate.

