### 5 PROTOCOL CLARIFICATIONS

The last secondary objective, estimation of healthcare resources cost, will not be calculated as stayed in section 3 of the protocol (3. Study objectives), since these variables were not The of Use collected in the CRF.

Adverse events were not collected in the study database and results regarding these variables will not be presented in the statistical report.

Secondary endpoint "Proportion of patients who guit their job due to IBD and have not been able to return to work" will not be calculated as stayed in section 10.1.1 of the protocol (10.1.1 Study endpoints), since these variables were not collected in the CRF

In the protocol the analysis dataset was not defined. In this SAP the analysis dataset was defined according to section 6 Definition of analysis subsets.

The descriptive analysis for continuous variables will be summarized by mean, standard variation, median, maximum, minimum as stayed in the protocol and also by first quartile and third quartile.

## 6

DEFINITION OF ANALYSIS SUBSETS only and Analysis dataset - All patients fulfilling selection criteria (section 4), who provided the written informed consent, without major study protocol deviations and who have completed the Day 1 assessment will be included in the statistical analysis dataset.

### RATIONALE AND CALCULATION OF THE SAMPLE SIZE 7

It is expected to include 246 patients regardless of IBD type.

This sample size will allow estimates with 95% confidence interval and a margin of error less than 5%, and assuming a rate of inadequate control of disease of 20% (conservative approach), regardless of IBD type. The following formula was used:

$$n = \frac{1.96^2 \times p \times (1-p)}{ME^2}$$

Rate of uncontrolled disease (p) = 20%

Margin of error (ME) = 0.05

Expected recruitment period: 6 months

ofUse

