### 8.1 **Primary Analyses**

The primary endpoint analysis will be performed calculating the proportion of patients with active disease at Day 1. The results will be presented as percentage and calculated as:

For Crohn's Disease (CD):

Number of patients with active CD (HBI score  $\geq 8$  or CDAI score  $\geq 220$ )  $p_{CD}$  = Total number of CD patients

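### 246 patients give the stated 5-point margin only for the pooled IBD proportion; at a 20% rate neither the CD nor the UC primary endpoint can reach it, and 20% is not conservative for precision

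*Protocol*

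**What the plan says.** The sample-size statement appears three times with the same content: in the Protocol 1.4 Summary (Number of subjects), in Protocol 10.6 and in SAP 7. SAP 7 says: "It is expected to include 246 patients regardless of IBD type". Protocol 10.6 gives the precision: "This sample size will allow estimates with 95% confidence interval and a margin of error less than 5" per cent. The Protocol Summary gives the assumption: "assuming a rate of inadequate control of disease of 20% (conservative approach), regardless of IBD type". All three use the single-proportion formula with p = 20% and a margin of 0.05. No source is given for the 20%.

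The primary objective (Protocol 1.4 and 3, SAP 2.1.1) is a single proportion among all IBD patients: "To evaluate the proportion of moderate to severe IBD patients with active disease at Day 1".

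The primary endpoints (Protocol 1.4 and 10.1.1, SAP 2.2.1) are two proportions: "For Crohn's Disease: Proportion of patients with active disease" and "For Ulcerative Colitis: Proportion of patients with active disease". SAP 8.1 opens with "The primary endpoint analysis will be performed calculating the proportion of patients with active disease at Day 1" and then gives one formula over all CD patients and another over all UC patients, as Protocol 10.2 does. Both sections add: "The 95% confidence intervals will be computed for each estimate". Neither gives a formula for total IBD. Total-IBD summaries are promised only by a general sentence covering every endpoint (Protocol 10.1.2, SAP 8).

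**The concern.** A sample size for a descriptive study is justified by the precision it gives the primary estimates. Here the calculation serves one pooled proportion, while the plan designates two type-specific proportions as primary. The margin is stated for unspecified estimates, so a reader could take it to cover the CD and UC results. Each of those will rest on only part of the 246 patients.

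The second problem is the word conservative. In this formula the variance term p(1-p) increases up to p = 50%, so any true rate between 20% and 80% gives a wider interval than planned, even pooled. Protocol 6.2 warns that patients with active disease attend more often and that disease control may therefore be underestimated. That moves the observed active rate up relative to the true rate, though it does not show that the rate exceeds 20%.

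At stake is whether the planned precision is described correctly, and whether the pooled estimate that answers the primary objective is actually specified.

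**Working it through.** **Inputs.** Total n = 246, p = 0.20, margin 0.05 and z = 1.96, from Protocol 10.6 and SAP 7. The documents plan no CD/UC split. The only local figure is the one-city UC:CD prevalence ratio of 7.04:1 in Protocol 2, used here as one illustration.

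**Step 1: reproduce the plan's figure.** n = 1.96² × 0.20 × 0.80 / 0.05² = 245.86, rounded up to 246. The inverse is half-width = 1.96 × √(p(1-p)/n). At n = 246 and p = 0.20 it gives 4.999 points. The stated number is correct for one proportion.

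**Step 2: apply it to the primary endpoints.** At n = 245 and p = 0.20 the half-width is already 5.009 points. If the sample contains at least one patient of each type, neither type can exceed 245, so neither can reach 5 points at 20%. This needs no assumption about the split. Reaching 5 points for both at 20% would take 246 + 246 = 492 patients.

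**Step 3: size of the shortfall.** The 7.04:1 ratio would give 246 × 7.04/8.04 = 215.4 UC and 246/8.04 = 30.6 CD, or about 215 and 31. Half-widths in percentage points:

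| Patients in the denominator | p = 20% | 30% | 40% | 50% |
|---|---|---|---|---|
| 246 (pooled) | 5.0 | 5.7 | 6.1 | 6.25 |
| 123 (each type, even split) | 7.1 | 8.1 | 8.7 | 8.8 |
| 172 (larger group, 74/172) | 6.0 | 6.8 | 7.3 | 7.5 |
| 74 (smaller group, 74/172) | 9.1 | 10.4 | 11.2 | 11.4 |
| 215 (UC, 7.04:1) | 5.3 | 6.1 | 6.5 | 6.7 |
| 31 (CD, 7.04:1) | 14.1 | 16.1 | 17.2 | 17.6 |

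The larger group can come close to 5 points at 20% while the smaller one is far from it. Conversely, 5 points is reached only if the true rate is at most about 16.8% with 215 patients, 8.8% with 123 or 2.1% with 31 (or correspondingly high, above 50%).

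**Step 4: is 20% conservative?** For a 5-point margin on one proportion the required n is 322.7 at 30%, 368.8 at 40% and 384.2 at 50%, against 245.86 at 20%. With n fixed at 246, the pooled half-width grows by at most 6.25 - 5.0 = 1.25 points.

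**Step 5: does the interval method matter?** The documents do not name one. With counts nearest 20%, the half-widths are:

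- 49/246: Wilson 4.97, exact 5.17.
- 25/123: Wilson 7.06, exact 7.46.
- 6/31: Wilson 13.6, exact 15.0.

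The pattern is the same under each method.

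**The case against.** The strongest reply is that pooled sizing was deliberate. The text says twice that the number applies whatever the IBD type, the primary objective is pooled, total-IBD summaries are planned for every endpoint, and no sentence promises 5 points for each type. That reading is reasonable and 246 is right under it. But it leaves the two named primary endpoints with no stated precision, and the estimate the study was sized for with no formula in either primary analysis section.

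A second reply is that little depends on this. That largely stands: no estimate is biased, no test or decision rule uses the 5-point margin, and each reported interval will show its real width. The SAP is dated August 2019 and refers in the past tense to variables not collected, so a change in recruitment is unlikely to be practical.

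Third, the 31/215 split is a thin scenario. It takes a ratio from one city, not described as limited to moderate-to-severe disease, and applies it to reference sites. With about 6 expected events the normal approximation is also rough. It is fair only as an outer illustration; the even split already makes the point.

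Fourth, a pooled proportion combines HBI or CDAI with partial Mayo cut-offs and is weighted by whatever mix is recruited. That is a reason to report it beside the CD and UC estimates, not in place of them.

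**Conclusion.** The concern holds. The figure of 246 is arithmetically correct, and its 5-point margin holds for the pooled IBD proportion at a 20% rate with all 246 evaluable. By the plan's own formula and at that rate, it holds for neither primary endpoint in any sample containing both types. The shortfall depends on the unplanned split: 7.1 points for each type if even, 9.1 and 6.0 at 74/172, and up to 14.1 for CD if the one-city ratio applied. Describing 20% as conservative is not correct for precision; the pooled cost is at most 1.25 points.

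The pooled margin also has no slack. The SAP 6 analysis set drops major deviators and patients without a completed Day 1 assessment, and one exclusion takes the half-width to 5.009 points.

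This should be corrected, but its consequence is limited to the stated planning precision.

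**What to change.** Recruit no further patients on this account. In the Protocol 1.4 Summary, Protocol 10.6 and SAP 7, replace the precision sentence with wording such as:

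> 246 evaluable patients give a 95% CI half-width of 5.0 points for the total-IBD proportion if the true rate is 20%, rising to 6.25 points at 50%; the CD and UC proportions will be less precise.

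Follow it with a short table of CD and UC half-widths over splits labelled as illustrative, for example 123/123, 74/172 and 31/215. Delete the conservative label or say in what sense it is meant.

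In Protocol 10.2 and SAP 8.1, add the total-IBD proportion with its 95% CI: active CD plus active UC patients, divided by all CD plus all UC patients. Identify it as the estimate that answers the pooled primary objective and that the sample size supports, and keep the CD and UC estimates beside it.

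Setting separate targets by type is the alternative, but at 20% it would double the study to 492 patients. The pooled objective does not require that.

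The cost is rewording in three places, one small table and one added formula in each document. The stated precision becomes less favourable; no data or visits are added.

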# **11 Reports**

A Non-Interventional Study Report based on the results obtained will be prepared and submitted for distribution. This Study Report should be available within one year from collection of the last data point, and the participating sites should be informed about the results when the report is finalized.

# **12** Publications

Takeda aims to have the results of this study published.

lercial

Takeda has the right to use the data and results for regulatory purposes and for internal presentation within the company and to partners.

# 13 Archiving of Study Documentation

During the course of the study the Study Site Responsible must as a minimum file the essential documents (Section 4.4), the protocol, any amendments, the list of participating subjects, the written informed consents, the CRFs and the progress reports in the Study Site File. After final database lock, the Study Site Responsible must keep a minimum store the list of participating subjects and the signed ICFs on site for 5 years. The Study Site Responsible should store additional study documentation for a Terms of Use longer period of time as required by any local regulations and/or hospital requirement.

### **REVISION LOG**

Version No.	Version Date	Author	Changes from Previous Approved Versions
1.0	28 AUG 2019	CCI	Not Applicable (First Version)
			10 x 0
			iicable
			3001
			, to the
			biect
			andst
		Ċ	M
		USE	
	~	ercitor	
	connti		
	r non		
\$ \$	KO.		
× 3KeOr			
5			

## 1 RATIONALE

This Statistical Analysis Plan (SAP) was written in accordance with CTI Clinical Trial & Consulting Services' standard operating procedure (SOP) ST.CO.01-01 for Biostatistics and intends to provide guidelines from which the analysis will proceed, create a common and clear understanding of the planned analysis by all involved, clarify issues which was not clarified in the protocol, expand statistical section of the protocol, provide basis for the statistical section of the statistical report and reduce the opportunity for bias by prospectively defining analysis. This SAP was prepared by the biostatistician who will be further responsible (if possible) for the statistical analysis of the study data.

This SAP, in particular table shells and examples of figures/graphs, was reviewed and approved by the Sponsor's Representative previously to database locking and performance of the statistical analysis.

Any changes to the planned statistical methodology here defined during the statistical analysis of the study data will be documented in the Statistical Report and in the Study Clinical Report.

This document was written in accordance with the information contained in the Study Protocol IBD-5004 - RISE AR, version 50, of 24 January 2018 and CRF Version 4.0, 18 December 2018.

# 2 STUDY OBJECTIVES AND ENDPOINTS

## 2.1 Objectives

## 2.1.1 Primary objective

To evaluate the proportion of moderate to severe IBD patients with active disease at Day 1 (active CD defined as Harvey Bradshaw Index [HBI] score  $\geq$  8 or Crohn's Disease Activity Index [CDAI] score  $\geq$  220 points; active UC defined as 9-point partial Mayo score  $\geq$ 5).

## 2.1.2 Secondary objectives

- To characterize socio-demographic and clinical aspects of moderate to severe IBD.
- To characterize treatment patterns for IBD during the 3 years previous to Day 1, including the use of biologic therapies and failure to these therapies (if any).

- For each IBD type, to compare patients with moderate to severe disease activity with patients with no or mild activity regarding socio-demographic and clinical variables of interest and treatment patterns.
- ms of Use To evaluate the quality of life (SF-36, EQ-5D and IBDQ) in moderate to severe IBD patients.
- To evaluate the work productivity impairment (WPAI) experienced by moderate to severe IBD patients.
- To describe the use of healthcare resources related with the management of IBD during the 3 years previous to Day 1.
- To estimate UC or CD-related healthcare costs during the 3 years previous to to the app Day 1.

### 2.2 Endpoints

### **Primary endpoints** 2.2.1

- For Crohn's Disease: Proportion of patients with active disease (HBI score  $\geq 8$ or CDAI score  $\geq$  220 points - based on criteria used by the site) at Day 1.
- For Ulcerative Colitis: Proportion of patients with active disease (9-point partial Mayo score ≥5) at Day 1.

